5.7 Concurrent Medications and Therapy

5.7.1 Background PAH Therapy

From the time of study entry, subjects are to remain on background PAH medical therapy with either a single agent or a combination of prostanoid, endothelin receptor antagonist, PDE-5 inhibitor, and/or guanylate cyclase stimulators as per the entry criteria. Doses must remain stable through the week 24 primary endpoint visit.

Investigational prostanoids, endothelin receptor antagonists and PDE-5 inhibitors are permitted if the drugs are already in use for the treatment of PAH but are not currently licensed for this use by the FDA.

Permitted Dose modifications:

- Toxicity management for any of the four classes of drugs
- Increase in prostacyclin dose of up to 10% for worsening disease independent of route of administration.

Other PAH medications, such as diuretics and anti-coagulation, should be managed by the treating physician according to institutional practice. Changes in diuretics and anti-coagulants are permitted throughout the duration of the study.

Stabilization/clinical improvement in PAH should result in no change to background therapy for the duration of the subject's participation in the study.

If a change in medical (beyond the 10% increase in prostacyclin dose) or surgical therapy is necessary for the treatment of progressive PAH before the week 24 primary endpoint visit then the subject will complete an Early Endpoint visit (see Section 6.5.6) and procedures in Section 3.3.2.1, *Follow-up Requirements for All Treated Subjects* numbers 2 and 3 will be followed.

After the week 24 endpoint visit, the doses of background therapies for PAH may be increased and other agents may be added as needed to treat worsening PAH if the subject experiences any one of the following:

- a deterioration in functional class and a decrease in 6MWD by $> 20\%$,
or
- the development of signs and symptoms of clinical right heart failure, such as worsening edema, ascites, and/or weight gain,
or
- other objective data suggesting clinical deterioration, such as worsening cardiopulmonary hemodynamics as evidenced by a $\geq 20\%$ decrease in cardiac output, a $\geq 20\%$ increase in mPAP, or a $\geq 20\%$ increase in PVR.

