4.3. Per Protocol Populations

The Per Protocol (PP) population will be defined as those subjects who comply with the assigned treatment protocol by completing two IV infusions of 1000mg of Rituximab/Placebo at Visit 3 and Visit 4 as well as completing primary endpoint evaluation (6MWD) at Visit 10 with no major protocol deviations that would affect their efficacy outcome. Subjects who are withdrawn from follow-up prior to Visit 10 will not be included in the PP population. A masked data review panel will evaluate deviations from the protocol including, for example, violations of entry criteria, departures from assigned treatment regimen, or administration of study procedures outside the specified visit windows. The panel may exclude subjects with serious protocol deviations from the PP population. Both the primary analyses and all secondary analyses will be replicated on the PP population.

A second Per Protocol (PP2) population will be also be defined. This population will be defined as eligible subjects who comply with the assigned treatment protocol by completing two IV infusions of 1000mg of Rituximab/Placebo at Visit 3 and Visit 4.

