7.3. Secondary Endpoints

All secondary analyses will be conducted in an exploratory fashion with p-values and confidence intervals presented as descriptive statistics with no adjustments for multiple comparisons. Interval estimates will be generated at the 95% confidence level. Analyses will be conducted on the ITT population and the PP populations. Missing data will not be imputed.

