7.3.3. Clinical Worsening

Endpoint: Assessment of time to clinical worsening, censored at 48 weeks, will be defined as first occurrence of the following: death, hospitalization for SSc-PAH, lung transplantation, atrial septostomy, addition of other PAH therapeutic agents, or worsening of 6MWD by > 20% and

an increase in functional class. The components of clinical worsening will be assessed as follows.

- a. Death: Date of death will be collected on the Post-Study Follow-Up/Week 104 Vital Status CRF page.
- b. Hospitalization for SSc-PAH: Date of hospitalization for SSc-PAH will be collected on the Serious Adverse Event CRF page and determined from SAEs that had seriousness criteria of “Required hospitalization or prolongation of existing hospitalization” and that were marked as being possibly, probably, or definitely related to worsening disease on the Adverse Events CRF page. Time to the event will be derived from the date that the AE became serious. If a subject has multiple hospitalizations for SSc-PAH, then the first date will be used.
 - i. A second clinical worsening endpoint will be similarly defined except that “hospitalizations for SSc-PAH” will be evaluated by a blinded review panel to exclude those events relating only to a subject’s SSc and not PAH.
- c. Lung transplantation: Date of lung transplant will be collected on the Initiation of New PAH Medications and Therapy CRF page.
- d. Atrial septostomy: Date of atrial septostomy will be collected on the Initiation of New PAH Medications and Therapy CRF page.
- e. Addition of other PAH therapeutic agents: Date of new medications or doses of PAH medications changed for the treatment of PAH will be collected on the Initiation of New PAH Medications and Therapy CRF page.

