- f. Worsening of 6MWD by > 20% and an increase in functional class: The 6MWD and the NYHA Functional Class Assessment will be performed at Screening and Weeks 4, 12, 24, 36, and 48; they may also be performed at an unscheduled visit. Data for the 6MWD will be collected on the 6-Minute Walk Test CRF page and data on functional class will be collected on the NYHA Functional Class Assessment CRF. The first date at which the 6MWD has decreased by >20% from the Screening walk distance and the NYHA Functional Class Assessment has increased a class from Screening will be recorded. If a subject’s 6MWD decreased from Screening by more than 20% and a repeat 6MWD was performed, then the better of the two values will be used in the analysis. If a subject is NYHA Class IV at baseline, then only a decrease of 20% in the 6MWD will be required.

Time to clinical worsening will be defined as the first date that meets any of the above criteria and will be calculated in study days as: date of first event – date of randomization. If a subject does not experience a relevant event by Week 48 or if the date of death is after the 48 week follow-up period, then time to clinical worsening will equal the duration of follow-up in the main study for that subject. Appropriate censor variables will be defined to indicate whether the time-to variable represents an event time or a censor time.

Analysis: Time to clinical worsening and type of clinical worsening reached will be summarized by treatment group and overall. Kaplan-Meier curves, including 95% confidence intervals, will be created for each treatment arm and will be compared using the log-rank test. A Cox proportional hazards model may be fit to assess the effect of treatment on time to clinical worsening, if appropriate. Additional covariates may be added to the model as appropriate. Analyses will be run using the definition of hospitalization of SSc-PAH as defined in both point B and B.i above.

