7.3.4. Addition of PAH medications

Endpoint: New medications or doses of PAH medications changed for the treatment of PAH will be collected on the Initiation of New PAH Medications and Therapy CRF page. Date of the

new or modified medication along with reason for the change will be collected for the first time a PAH medication is modified or added.

Indicator variables for new or modified PAH therapeutic agents will be derived for two time points: prior to Week 24 and after Week 24. Time to the addition or modification of PAH medications will be defined in study days as: date of the first time a PAH medication is modified or added – date of randomization.

Analysis: The number and proportion of subjects who changed or added PAH therapeutic agents prior to Week 24 and after Week 24 will be summarized by treatment group and overall, along with the reason for changes to the background PAH medications. Time (in days) to the addition or modification of PAH medications will also be summarized by treatment group and overall.

Kaplan-Meier curves, including 95% confidence intervals, will be created for each treatment arm and will be compared using the log-rank test.

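### The Per Protocol set requires the Week 24 walk, so the Per Protocol reruns of time to clinical worsening and PAH-medication change drop early deaths and, on the natural reading, early rescues because they had the event

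*SAP*

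**What the plan says.** **Membership.** SAP 4.3 defines PP as subjects who received both infusions "as well as completing primary endpoint evaluation (6MWD) at Visit 10 with no major protocol deviations that would affect their efficacy outcome". It adds: "Subjects who are withdrawn from follow-up prior to Visit 10 will not be included in the PP population". Protocol 8.2.3 has the same rule. A second set, PP2, asks only for eligibility and two completed infusions.

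**Use.** SAP 4.3 states: "Both the primary analyses and all secondary analyses will be replicated on the PP population". SAP 7.3 says of the secondary endpoints: "Analyses will be conducted on the ITT population and the PP populations". Protocol 8.3.2.2 also repeats all its analyses on PP. Neither SAP 7.3.3 nor SAP 7.3.4 is exempted.

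**Endpoints.** Clinical worsening (SAP 7.3.3) is the "first occurrence of the following: death, hospitalization for SSc-PAH, lung transplantation, atrial septostomy, addition of other PAH therapeutic agents", or a walk decline of more than 20% with a worse functional class. Time runs as "date of first event – date of randomization". SAP 7.3.4 analyses PAH-medication change as proportions before and after Week 24 and as a time to event ("Time to the addition or modification of PAH medications will be defined in study days as", again from randomization), with Kaplan-Meier curves and a log-rank test.

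**What early rescue does to follow-up.** If progressive PAH needs a therapy change before Week 24, beyond a 10% prostacyclin increase, protocol 5.7.1 says "then the subject will complete an Early Endpoint visit (see Section 6.5.6) and procedures in Section 3.3.2.1", items 2 and 3. Item 1 of 3.3.2.1 keeps the full visit schedule for subjects who do not need prohibited therapy for progression. Item 3 leaves B-cell checks and Grade 3 or higher infections. Protocol 6.5.6 describes the Early Endpoint visit as the visit for subjects who withdraw early.

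**The concern.** A per protocol set is meant to select on adherence. For these two endpoints, this one selects on the outcome. A subject who dies in Week 10 cannot walk at Week 24. A subject rescued for progression in Week 10 is routed out of the schedule before Week 24. Each is an event in the ITT analysis and absent, event and person alike, from the PP analysis. Those who remain are credited with 24 weeks at risk during which such events could not be observed.

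The SAP recognises this problem elsewhere. Its note in 7.3.1 warns that PVR results may be biased towards subjects who reached Week 24. No such warning appears where early loss is itself the endpoint.

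At stake is how the PP result is read beside ITT. Lower PP curves could be taken as reassurance about worsening. A PP difference smaller or larger than the ITT one could be taken as evidence about robustness, when it may only reflect who was allowed into the set.

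**Working it through.** **1. The plan's own figures.** The documents give no event rate or power for either time-to-event endpoint. The one main-trial power figure for the current design (protocol 8.1: 33 m, SD 58 m, 20% dropout) reproduces. With 30 × 0.8 = 24 per arm, 33 / (58 × √(2/24)) = 1.971, and Φ(1.971 − 1.960) ≈ 50.4%, against 50% stated. The point does not rest on it; only the 30 per arm is used below.

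**2. Which early events can appear in PP.**

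| Event before Week 24 | Can the subject be in PP? |
|---|---|
| Death | No |
| Therapy change for progression leading to an Early Endpoint visit | No, on the natural reading |
| Prostacyclin increase of up to 10% for worsening disease | Yes (permitted in protocol 5.7.1) |
| Toxicity-driven switch | Yes (protocol 3.3.2.1 keeps full follow-up) |
| Hospitalization without therapy change | Yes |
| Walk and functional-class decline without therapy change | Yes |

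**3. Size, under stated assumptions.** Let *e* be an arm's risk by Week 24, *t* its risk by Week 48, and *f* the fraction of early events that bar the subject from PP. Then

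- PP 24-week risk = e(1 − f) / (1 − f·e)
- PP 48-week risk = (t − f·e) / (1 − f·e)

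Assume a placebo 48-week risk of 40% at constant hazard. Placebo Week 24 survival is √0.6 = 0.7746, so e = 22.5%. With f = 0.75, PP 24-week risk = 0.2254 × 0.25 / (1 − 0.1691) = 6.8%, and PP 48-week risk = (0.400 − 0.1691) / 0.8309 = 27.8%.

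Rituximab risks before selection:

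- Early-only benefit (HR 0.3, then 1.0): e = 1 − 0.7746^0.3 = 7.4%; t = 1 − 0.9262 × 0.7746 = 28.3%.
- Constant HR 0.5: e = 1 − 0.7746^0.5 = 12.0%; t = 1 − 0.7746 = 22.5%.
- Delayed benefit (HR 1.0, then 0.3): e = 22.5%; t = 28.3%.

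Placing each in the second formula gives the 48-week difference, placebo minus rituximab, in percentage points:

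| Timing of effect | All treated | PP, f = 0.60 | PP, f = 0.75 | PP, f = 1 |
|---|---|---|---|---|
| Early only | 11.7 | 5.7 | 3.7 | 0 |
| Constant | 17.5 | 14.1 | 12.9 | 10.6 |
| Delayed | 11.7 | 13.6 | 14.1 | 15.2 |

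Placebo 24-week risk in PP is 10.4%, 6.8% and 0% for the three values of f, against 22.5% for all treated subjects.

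**4. Events lost.** Count only events that bar PP entry (f = 1), with 30 per arm, constant HR 0.5 and an assumed placebo 24-week risk of 10%, 20% or 30%. At 20%, expected events to Week 48 are 30 × (1 − 0.64) + 30 × (1 − 0.80) = 10.8 + 6.0 = 16.8. Those before Week 24 are 30 × 0.20 + 30 × (1 − √0.80) = 6.0 + 3.2 = 9.2, or 55%. At 10% the loss is 4.5 of 8.7 (52%); at 30% it is 13.9 of 24.3 (57%).

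**5. Are early events plausible?** Protocol 1.1 cites one-year SSc-PAH survival of 50–81%. At constant hazard that implies 1 − 0.81^(24/52) = 9% to 1 − 0.50^(24/52) = 27% mortality by Week 24. These are background cohorts and trial subjects may do better, so this is not a forecast.

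**The case against.** The other side has a good case, and most of it limits the point rather than removing it.

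- *The affected analysis is minor.* ITT leads (SAP 4.2), PP2 is already planned, secondary p-values are descriptive, and no decision rule uses PP. SAP 5.1 reports numbers in each set, reasons for early termination, and a per-subject graph of death, withdrawal and first medication change, so the exclusions will be visible. This stands.
- *Exclusion of every rescue is an inference.* The Early Endpoint visit includes a walk, and protocol 8.5.5 lets that walk contribute to the Week 24 estimate; SAP 4.3 does not say whether it counts for PP. Protocol 5.6 treats prohibited changes as either deviations or reasons for early endpoint, so some rescued subjects might reach Visit 10, though the review panel could still exclude them as deviations. This stands as a caveat. The exclusion of subjects withdrawn before Visit 10, read with protocol 6.5.6, makes removal the likelier reading. Exclusion of early deaths is not in doubt.
- *The direction is not fixed.* Protocol 1.5 says B-cell depletion may not act immediately, and under delayed benefit PP enlarges the difference. This stands.
- *PP2 is also conditional.* It drops anyone who dies or progresses before the second infusion. True, but that window is about 2 to 4 weeks (protocol 5.3.6), not 24.

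A reader might infer that PP contains no progression-driven medication change before Week 24. The permitted prostacyclin increases show otherwise. A reader might also infer that the trial's survival analysis is compromised. Time to all-cause mortality (SAP 8.3.2) is a safety analysis on the Safety Population (SAP 8.1), which has no Visit 10 condition; death is affected only as a component of clinical worsening.

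**Conclusion.** The concern holds for the PP replicates of SAP 7.3.3 and 7.3.4. PP entry depends on an event-related condition 24 weeks after the clock starts. Early deaths are certainly removed, and rescues leading to an Early Endpoint visit very probably are. Absolute risk is understated in both arms. The distortion of the treatment comparison has no fixed sign: in the illustration with f = 0.75, the 48-week difference falls by 8.0 points (early-only benefit), falls by 4.6 (constant hazard ratio) or rises by 2.4 (delayed benefit).

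These sizes rest on assumed event rates, removal fractions and hazard ratios, because the documents give none. It would be tempting to say that PP erases a treatment effect. That follows only if all benefit falls before Week 24 and every early event bars entry. The ITT analyses, the primary endpoint and the mortality analysis do not share this defect. It is worth correcting because the remedy is nearly free, but it does not threaten the trial's main conclusions.

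**What to change.** In SAP 4.3 and 7.3, state that time to clinical worsening (7.3.3) and PAH-medication change (7.3.4, both the time to event and the proportions) are analysed on ITT and PP2 only, and that PP is kept for endpoints measured at Week 24. Align protocol 8.2.3 and 8.3.2.2, or list the departure in SAP section 11. Add one sentence saying that PP2 still conditions on reaching the second infusion, so a small residual selection remains.

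The cost is a few sentences and fewer tables. No new data are needed, and no sample-size or power figure changes.

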5. STUDY SUBJECTS

5.1. Disposition of Subjects

The disposition of all enrolled subjects will be summarized in tables and listed.

The numbers and percentages of subjects randomized, in each analysis sample, and completing selected study weeks (Day 0; Weeks 2, 24 and 48), as well as reasons for early termination from the study will be presented. For subjects discontinuing study treatment early, the reasons for discontinuing study treatment early will also be presented.

Subject status will also be shown graphically by subject. Each subject will be represented by a line with events such as treatment, early study withdrawal, first addition/change in PAH medications, death, etc. shown over time in the study.

5.2. Demographic and Other Baseline Characteristics

Summary descriptive statistics for baseline and demographic characteristics will be reported for all analysis samples. Characteristics to be summarized include: age, race, ethnicity, sex, body weight and height at screening, duration of SSc-PAH disease, PVR (by type), right atrial mean pressure, mean pulmonary artery pressure, cardiac output, pulmonary capillary wedge mean pressure, 6MWD, NYHA Functional Class, digital ulcer count, DLCO, FVC, TLC, HAQ-DI score, oxygen saturation, autoantibody status, number of PAH medications, oxygen use, limited or diffuse SSc, duration of SSc, smoking history, and BNP/pro-NTBNP.

Demographic and baseline characteristic data will also be presented in data listings by treatment group and subject.

6. STUDY OPERATIONS

6.1. Protocol Deviations

Major protocol deviations will be listed by site with information such as type of deviation, whether notification to the IRB was required, date of occurrence, and the reason for the deviation. Protocol deviations will be summarized in tabular format by type of deviation.

6.2. Treatment Adherence

Subjects will be randomized into either the rituximab or placebo arm. Rituximab or placebo will be administered as two IV infusions of 1000 mg each, given two weeks apart at Day 0 and Week 2. Study treatment information is collected on the Rituximab/Placebo Infusion CRF page. Percent compliance for study drug (rituximab or placebo) will be computed for both study visits and overall as:

$$\% \text{ Compliance} = \frac{\text{Total dose received (mg)}}{\text{Total dose planned (mg)}} \times 100$$

Where:

$$\text{Total dose received (mg)} = \text{concentration of infusion (mg/mL)} \times \text{total volume infused (mL)}$$

For each study arm and overall, percent compliance for study drug will be summarized descriptively by mean, standard deviation, median, minimum and maximum.

Compliance data for study drug will be listed by treatment group, subject, and infusion visit and will include use of pre-infusion medications, duration of infusion, information on incomplete or interrupted infusions, actual and planned dose, as well as concomitant therapy during study drug administration.

7. ENDPOINT EVALUATION

7.1. Overview of Efficacy Analysis Methods

7.1.1. Multicenter Studies

Due to the small sample size and large number of sites needed for this study, study center will not be included as a covariate in the analysis. However, if evidence of a study center effect exists and there are appropriate sample sizes at each site, a sensitivity analysis will be performed including study center in the efficacy analyses. All safety analyses will be based on data pooled across all centers with no adjustment or stratification by center.

7.1.2. Assessment Time Windows

Allowable visit windows for all scheduled visits are provided in Table 7-1.

Table 7-1 Visit Windows

Visit	Window
Screening	-28 Days
Baseline	-7 Days
Day 0	
Week 2	± 4 Days
Weeks 4, 8, 12, 16, 20, 24, 28, 32, 36, 40, 44, 48	± 7 Days
Quarterly Monitoring	± 14 Days

Unscheduled visits may also occur throughout the study. All data will be included in analyses, regardless of time of assessment.

7.2. Primary Endpoint

7.2.1. Computation of the Primary Endpoint

The primary efficacy endpoint is change in exercise capacity, assessed by the Six Minute Walk Distance (6MWD), from baseline to 24 weeks after treatment initiation. The 6MWD will be performed at Screening and Weeks 4, 12, 24, 36, and 48; additionally, if the 6MWD decreased from the Screening 6MWD by more than 20%, a subject should repeat the 6MWD within 7 days, but not on the same day. A 6MWD may also be performed at an unscheduled visit.

The 6MWD measures the distance a subject is able to walk over a total of six minutes on a hard, flat surface. The goal is for the subject to walk as far as possible in six minutes. The subject is allowed to self-pace and rest as needed as they traverse back and forth along a marked walkway. The total distance walked, in meters, will be recorded for each subject on the 6-Minute Walk Test CRF page. Information on whether a subject has a musculoskeletal disorder that limits ambulation (yes/no) will also be collected on this CRF page.

If a subject's 6MWD decreased from Screening by more than 20% and a repeat 6MWD was performed, then the better of the two values will be used in the primary analysis. Missing data will not be imputed.

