2.1 Primary Objective

- To compare patients with SSc-PAH treated with rituximab to those on placebo for change in exercise capacity, as determined by 6-minute walk distance (6MWD).

Hypothesis: The treatment group will demonstrate improvement or stabilization relative to the placebo arm in 6MWD from baseline to 24 weeks post-treatment initiation.

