6.5.4.6 Week 24 ± 7 days (Visit 10)

Assessments:

- Full Physical Examination with Vital Signs
- NYHA Functional Class Assessment
- Right heart catheterization: The subject should be on the same amount of supplemental oxygen used during the Screening RHC unless safety will be impacted. The methods of calculating pulmonary capillary wedge mean pressure and cardiac output should be the same as that used for the Screening RHC and, if feasible, the procedure should be scheduled at approximately the same time of day as the Screening RHC.
- Pulmonary Function Tests: DLCO only
- Oxygen Saturation (forehead or ear probe must be used for saturations < 95% by finger probe). Measure first at room air, then add/titrate oxygen if needed to maintain O₂ saturation ≥ 90%. The room air oxygen saturation measurement will be conducted at the discretion of the study physician. The measurement should not be performed if subject safety will be compromised.
- SF-36
- SHAQ

- 6MWT: The subject should complete the assessment with the same amount of supplemental oxygen used to complete the Screening 6MWT unless safety will be impacted (if the 6MWD *decreased* from the Screening 6MWD by more than 20%, repeat the 6MWT within 7 days, but not on the same day)
- Digital Ulcer Count
- Hematology: CBC with differential count and platelet count (hematocrit, hemoglobin, platelets, WBC, bands, eosinophils, lymphocytes, monocytes, neutrophils)
- Chemistry: albumin, alkaline phosphatase (ALP), ALT/SGPT, AST/SGOT, BUN, creatinine, potassium, sodium, total and indirect bilirubin, total CO₂, total protein, BNP/NT-proBNP
- CD19+ B cell studies
- Autoantibodies
- Serum Immunoglobulins
- IL-1, IL-6, and other cytokine assays
- HACA and rituximab serum level (PK). Batched and sent to Covance Laboratories.
- Concomitant Medication Assessment
- Adverse Event Assessment

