The 6MWD has been the most utilized endpoint in PAH trials, and a 33m improvement from baseline is considered clinically significant [160]. For sample size calculations, we assume a change from baseline of 0m for the placebo arm and 33m for the rituximab arm. An effect size of this magnitude is attainable in a 24 week period, and has been seen in as little as 12 weeks in studies using vasodilators. Assuming a standard deviation of 58m (a best guess based on prior studies) and a 20% drop out rate, ASC01 would be powered at 50% to detect a treatment group difference of 33m for this phase II study. If a significant result is found for this primary efficacy endpoint and no safety signals emerge, this study could provide a definitive conclusion about this treatment. In order to achieve 80% power, the true difference between treatment groups would have to be at least 50m. While other studies evaluating other drugs have seen this magnitude of difference in similar timeframes, we have no data on rituximab to suggest the true difference is at least 50m. Furthermore, rituximab would be interesting as a therapy option if the effect size is as small as 33m.

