7.2.2. Primary Analysis of the Primary Endpoint

The primary efficacy analysis for this study is designed to test the scientific hypothesis that rituximab has a beneficial clinical impact on SSc-PAH as measured by improvement or stabilization in 6MWD between baseline to 24 weeks in patients treated with standard of care plus rituximab than in patients treated with standard of care plus placebo. Operationally for this study, this scientific hypothesis will be examined by formally testing the following statistical hypothesis:

H_0 : The mean change in 6MWD between baseline and 24 weeks does not differ between individuals treated with rituximab and those treated with placebo
($\bar{\delta}_{\text{rituximab}} = \bar{\delta}_{\text{placebo}}$ where $\bar{\delta}_x = \text{mean 6MWD at 24 weeks} - \text{mean 6MWD at baseline}$)

versus

H_A : The mean change in 6MWD between baseline and 24 weeks is more beneficial in those individuals treated with rituximab than in those treated with placebo
($\bar{\delta}_{\text{rituximab}} < \bar{\delta}_{\text{placebo}}$ where $\bar{\delta}_x = \text{mean 6MWD at 24 weeks} - \text{mean 6MWD at baseline}$)

While this hypothesis is inherently one-sided, a two-sided test at $\alpha=0.05$ will be used to evaluate the treatment effect at 24 weeks. This primary hypothesis will be tested using a repeated measures random effect model to model the distance walked as a function of treatment, visit week and a treatment by visit week interaction. Additionally, a quadratic term for visit week will be included in the model. A random slope and intercept will be fit for each subject using a separate unstructured covariance matrix for each treatment group. The model will include only 6MWD data up to Week 24. All available data up to Week 24 will be used for subjects who terminate early from the study. All unscheduled visits that occur prior to Week 24 will also be included in the analysis.

Model estimates and standard errors of the distance walked and change from baseline in distance walked will be presented at baseline and Week 24, along with the differences between arms. An appropriate contrast will be used to test the difference (baseline to Week 24) between treatment arms.

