7.2.3. Sensitivity Analyses of the Primary Endpoint

The following sensitivity analyses will be performed:

1. Primary analyses performed on both PP populations.
2. If a subject's 6MWD decreased from Screening by more than 20% and a repeat 6MWD was performed, then models will be developed using both 6MWD values and also using just the second, confirmatory, value in the model.
3. Changes in background PAH medications prior to Week 24 (yes/no) will be added as a covariate to the model.
4. Missing data will not be imputed for the primary endpoint. However, sensitivity analyses may be performed to assess the robustness of the conclusions under different

assumptions. For example, missing data due to death of a subject prior to Week 24 would be handled differently than missing data due to a missed visit. A joint longitudinal/survival model to evaluate trends in clinical assessments under different assumptions about the underlying missing data mechanism may be considered, if appropriate.

5. Demographic and baseline characteristics that differ meaningfully between the two treatment groups (with or without a p-value <0.05) may be included in a covariate-adjusted model, as appropriate.
6. Time-varying covariates, like oxygen use during SMWD, may be added as appropriate.

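### The primary 6MWD analysis replaces a low walk with the better of two only after a fall of more than 20%, which shrinks a true arm difference by a few metres when the arms have similar spread

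*SAP*

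**What the plan says.** The Protocol's visit schedule, for example 6.5.4.6 (Week 24), tells a subject whose walk has dropped more than 20% below the Screening walk to "repeat the 6MWT within 7 days, but not on the same day". It does not say which of the two walks is analysed. SAP 7.2.1 fills that gap: when a repeat was done after such a fall, "then the better of the two values will be used in the primary analysis". No matching rule exists for an unusually high walk, and the Screening walk is a single attempt.

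SAP 7.2.2 defines H0 through the arm means of 6MWD at 24 weeks minus baseline and specifies that a "two-sided test at $\alpha=0.05$ will be used to evaluate the treatment effect at 24 weeks". The model uses a random intercept and slope per subject with a separate covariance matrix for each arm, takes walks only through Week 24, and keeps walks from unscheduled visits before then.

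SAP 7.2.3 item 2 already plans two checks on this rule: "then models will be developed using both 6MWD values and also using just the second, confirmatory, value in the model". No planned model uses the scheduled walk alone for all subjects.

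**The concern.** Subjects qualify for a second attempt partly because of a chance low first attempt, and the higher of the two is then kept. Their analysed value is raised on average, and nobody else's is. If one arm has more decliners, that arm receives more of the lift and the arm contrast no longer estimates the difference in mean change. This matters most for the estimate and its interval. Protocol 8.1 says "ASC01 would be powered at 50% to detect a treatment group difference of 33m", so interpretation will rest heavily on how large the effect appears and not only on whether the test is significant. The Protocol's hypothesis also allows for a placebo arm that worsens: "The treatment group will demonstrate improvement or stabilization relative to the placebo arm in 6MWD from baseline to 24 weeks post-treatment initiation". That is the setting with most repeats.

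**Working it through.** **Inputs from the documents.** Protocol 8.1: "we assume a change from baseline of 0m for the placebo arm and 33m for the rituximab arm"; "Assuming a standard deviation of 58m (a best guess based on prior studies) and a 20% drop out rate". There are 30 subjects per arm, so 30 x 0.8 = 24 per arm after dropout. Alpha is 0.05 two-sided. Screening 6MWD is at least 100 m (Protocol 4.1).

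**Inputs assumed.** Screening mean 300 to 400 m, Screening SD 100 m, test-retest SD 15 to 40 m. A repeat is always done when triggered, and the two walks have independent test-retest errors.

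**Step 1: the plan's own power figure.** SE = 58 x sqrt(2/24) = 16.74 m. 33/16.74 = 1.971, and Phi(1.971 - 1.960) = 50.4% (noncentral t: 48.8%). The stated 50% is reproduced.

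**Step 2: the form of the bias.** Let B be Screening, Y1 the scheduled walk and Y2 the repeat. The analysed value is Y1 if Y1 >= 0.8B, and max(Y1, Y2) otherwise. The lift in an arm is

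L = P(Y1 < 0.8B) x E[max(Y2 - Y1, 0) given Y1 < 0.8B], which is never negative.

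The bias in the arm difference is L(rituximab) - L(placebo). It is zero when the arms have the same distribution. With equal spread, the arm that does worse has the larger L, so the difference shrinks. With unequal spread, the arm with the wider spread can have the larger L whatever the treatment effect.

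**Step 3: size at Week 24.** Simulation with 2,000,000 subjects per arm. The between-subject variance of true change is 58^2 - 2s^2, where s is the test-retest SD, so the observed SD of change stays at 58 m. Screening mean 350 m:

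| Placebo / rituximab change (m) | s (m) | Repeats, placebo / rituximab | Scheduled walk (m) | Better of two (m) | Loss (m) |
|---|---|---|---|---|---|
| 0 / 0 | 25 | 11.8% / 11.8% | 0.05 | 0.04 | 0.0 |
| 0 / +33 | 25 | 11.8% / 4.1% | 33.03 | 31.31 | 1.7 |
| -33 / 0 | 15 | 26.9% / 12.3% | 32.94 | 31.48 | 1.5 |
| -33 / 0 | 25 | 26.5% / 11.8% | 32.98 | 30.24 | 2.7 |
| -33 / 0 | 35 | 25.9% / 11.2% | 32.96 | 28.70 | 4.3 |
| 0 / -33 (harm) | 25 | 11.8% / 26.5% | -33.08 | -30.33 | 2.7 toward zero |

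Over Screening means of 300 to 400 m and s of 20 to 40 m, the loss is 1.0 to 4.1 m for 0 vs +33 (1.0/33 = 3% to 4.1/33 = 12%). For -33 vs 0 it is 1.8 to 5.6 m (5% to 17%).

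**Step 4: unequal spread** (s = 25 m, mean 350 m). With no true difference, an SD of change of 50 m on placebo and 70 m on rituximab gives +1.1 m in favour of rituximab. Reversing the spread (70 and 50 m) gives -1.2 m. With SDs of 45 and 90 m, a true 33.1 m becomes 33.7 m.

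**Step 5: the longitudinal model.** Random intercept and slope, a quadratic week term, weeks 0, 4, 12 and 24, rule applied at every visit, known variances, mean 350 m, 0 vs +33. At s = 15, 25 and 35 m the Week 24 contrast goes from 33.2, 33.0 and 33.1 m (scheduled walk) to 32.3, 31.2 and 30.3 m (better of two).

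**Step 6: power.** The rule also narrows the spread. For -33 vs 0 at s = 35 m, the SD of change falls to about 51.6 m: SE = 51.6 x sqrt(2/24) = 14.90 m, 28.70/14.90 = 1.927, and Phi(1.927 - 1.960) = about 49%, against about 50% with the scheduled walk. Over s of 15 to 35 m the loss is about 2 points or less.

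**Step 7: the planned alternatives.** Second value only gives 30.4 to 32.6 m for 0 vs +33, so it removes only part of the shrinkage. With both values in the model (24 per arm, s = 20, 30 and 40 m), the estimates are 32.7, 32.1 and 33.2 m. Scheduled-only gives 32.8, 32.2 and 33.2 m on the same data, and better-of-two gives 31.4, 30.0 and 29.4 m.

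**The case against.** The rule is pre-specified, applies identically to both blinded arms and has two sensitivity models already planned. The test asks subjects to walk as far as they can, so taking the better attempt after an apparent drop is a defensible reading of capacity. The typical loss is a few metres, and every figure depends on a test-retest SD and a Screening mean that the documents do not supply. All of this is fair, and it limits the size of the point. It does not remove it: equal application does not give equal lift when the arms differ, and a sensitivity model does not correct the primary estimate.

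Four stronger readings are tempting and are not supported.

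- **That the rule always pulls toward zero.** Steps 3 and 4 show no bias with equal arms and equal spread, and a shift in either direction with unequal spread, which the SAP's arm-specific covariance allows.
- **That it costs substantial power.** The SD falls along with the estimate. Calculations that hold the variance at its original value exaggerate the loss.
- **That it is an undeclared change from the Protocol.** Protocol 8.3.2.1 leaves analysis details to the SAP, 8.5.6 asks only for major changes to be noted, and the Protocol never says which walk counts. Its absence from SAP Section 11 is not a fault.
- **That the planned both-values model is simply the unbiased answer.** That holds only if the two walks are independent given the random intercept and slope. If they share a short-term deviation, such as an intercurrent illness, the low visit is counted twice. With a test-retest SD of 15 to 20 m and a shared SD of 25 to 30 m, the estimate was inflated by about 0.6 to 1.0 m. A Week 24 repeat taken up to 7 days later also sits awkwardly with the model's Week 24 data limit.

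**Conclusion.** The concern holds in a limited form. The rule is one-sided and conditioned on the outcome, so the primary model does not estimate the mean change that H0 defines. Given a true 33 m difference and similar spread in the arms, the estimate is too small by about 1 to 4 m (0 vs +33) or about 2 to 6 m (placebo declines by 33 m, rituximab stable). A harmful effect would be understated in the same way. These figures rest on the assumed Screening mean of 300 to 400 m and test-retest SD of 20 to 40 m. The null case with equal spread is unaffected and the power cost is small, so the damage is to the point estimate and interval. Only the lower of a pair of walks is dropped. A low scheduled walk stays if no repeat was done or the repeat was lower still. The correction is worth making because it is nearly free and the direction of the shift cannot be guaranteed in advance.

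**What to change.** In SAP 7.2.1, replace the better-of-two sentence with: *The scheduled 6MWD at each visit is used in the primary analysis for all subjects; repeat walks triggered by a fall of more than 20% are not used in the primary model.* State that this exclusion does not cover walks at other unscheduled visits, which stay in the model under 7.2.2.

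In 7.2.3 item 2, list better-of-two, both-values and second-value-only as sensitivity analyses. Note that better-of-two and second-value-only shrink a true difference when spread is similar, and that both-values is unbiased only if the two walks are conditionally independent given the random effects. Say how a repeat of the Week 24 walk is dated in these models. Better-of-two can stay in 7.3.3(f), where it confirms an event.

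The cost is SAP wording and one re-ordering of analyses, with no new data. The downside is that a single bad-day scheduled walk remains in the primary model. It is then treated like any other chance low or high walk in either arm.
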